Patients should not receive treatment with medications with a possible or conditional risk of causing Torsades de Pointes, or those associated with prolongation of the QT interval unless medically necessary. If medically necessary, close follow up and monitoring is recommended.

All medications (other than study drug) and significant non-drug therapies administered after the patient starts treatment with study drug, with any changes in dosing must be recorded in the electronic medical record.”

Erythropoietin, granulocytic or other hematopoietic colony stimulating factors for treatment of cytopenias are discouraged. If administered, the subject will not be eligible for a hematologic improvement (HI) response assessment within 2 weeks of administration.

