10.0 CRITERIA FOR RESPONSE

The primary endpoint is the overall response rate (ORR) per IWG-2006 criteria¹³. This is summarized in table 9 and 10. Response will include complete remission, partial remission, marrow complete remission and any hematological improvement achieved any time during the duration of the therapy.

Table 9. Proposed modified International Working Group response criteria for altering natural history of MDS⁷

Category	Response criteria (responses must last at least 4 wk)
Complete remission	Bone marrow: ≤5% myeloblasts with normal maturation of all cell lines

	
Persistent dysplasia will be noted[†]
 
Peripheral blood[‡]
 
 • Hgb ≥ 11 g/dL • Platelets $\geq 100 \times 10^9/L$ • Neutrophils $\geq 1.0 \times 10^9/L$[†] • Blasts 0%
Partial remission	
All CR criteria if abnormal before treatment except:
 
 • Bone marrow blasts decreased by $\geq 50\%$ over pretreatment but still $> 5\%$ • Cellularity and morphology not relevant
Marrow CR [†]	
Bone marrow: $\leq 5\%$ myeloblasts and decrease by $\geq 50\%$ over pretreatment[†]
 
Peripheral blood: if HI responses, they will be noted in addition to marrow CR[†]

Stable disease	
Failure to achieve at least PR, but no evidence of progression for > 8 wks

Failure	
Death during treatment or disease progression characterized by worsening of cytopenias, increase in percentage of bone marrow blasts, or progression to a more advanced MDS FAB subtype than pretreatment

Relapse after CR or PR	
At least 1 of the following:
 
 • Return to pretreatment bone marrow blast percentage • Decrement of $\geq 50\%$ from maximum remission/response levels in granulocytes or platelets • Reduction in Hgb concentration by ≥ 1.5 g/dL or transfusion dependence
Cytogenetic response	
Complete
 
 • Disappearance of the chromosomal abnormality without appearance of new ones 
Partial
 
 • At least 50% reduction of the chromosomal abnormality

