Disease progression	
For patients with:
 
 • Less than 5% blasts: $\geq 50\%$ increase in blasts to $> 5\%$ blasts • 5%-10% blasts: $\geq 50\%$ increase to $> 10\%$ blasts • 10%-20% blasts: $\geq 50\%$ increase to $> 20\%$ blasts • 20%-30% blasts: $\geq 50\%$ increase to $> 30\%$ blasts 
Any of the following:
 
 • At least 50% decrement from maximum remission/response in granulocytes or platelets • Reduction in Hgb by ≥ 2 g/dL • Transfusion dependence
Survival	
Endpoints:
 
 • Overall: death from any cause • Event free: failure or death from any cause • PFS: disease progression or death from MDS • DFS: time to relapse

- Cause-specific death: death related to MDS

Table 10. Proposed modified International Working Group response criteria for hematologic improvement⁷

Hematologic improvement [*]	Response criteria (responses must last at least 8 wk) [†]
Erythroid response (pretreatment, < 11 g/dL)	Hgb increase by ≥ 1.5 g/dL Relevant reduction of units of RBC transfusions by an absolute number of at least 4 RBC transfusions/8 wk compared with the pretreatment transfusion number in the previous 8 wk. Only RBC transfusions given for a Hgb of ≤ 9.0 g/dL pretreatment will count in the RBC transfusion response evaluation [†]
Platelet response (pretreatment, < $100 \times 10^9/L$)	Absolute increase of $\geq 30 \times 10^9/L$ for patients starting with $> 20 \times 10^9/L$ platelets Increase from $< 20 \times 10^9/L$ to $> 20 \times 10^9/L$ and by at least 100% [†]
Neutrophil response (pretreatment, < $1.0 \times 10^9/L$)	At least 100% increase and an absolute increase $> 0.5 \times 10^9/L$ [†]
Progression or relapse after HI [‡]	At least 1 of the following: At least 50% decrement from maximum response levels in granulocytes or platelets Reduction in Hgb by ≥ 1.5 g/dL Transfusion dependence

Secondary endpoints include:

1. To evaluate efficacy of Pacritinib based on the presence of JAK2 and FLT3 mutations at diagnosis.
2. To evaluate efficacy based on IPSS, R-IPSS and LR-MDS risk classification systems at diagnosis.

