12.0 STATISTICAL CONSIDERATIONS

General Description

This is a Phase II open-label study designed to evaluate the efficacy and toxicity of Pacritinib as single agent (Part 1) and Pacritinib + HMA (Part 2) in subjects with lower-risk myelodysplastic syndrome. The primary efficacy outcome of both parts is the overall response rate (ORR) based mainly on hematologic improvement defined by IWG-2006 criteria, and which also includes complete remission (CR), partial remission (PR) and marrow complete remission. In Part 1, patient's overall response will be assessed after 1 cycle of treatment but no more than after 4 cycles of treatment; cycle length is 28 days. If no response is attained after 4 cycles of treatment or if progression occurs during therapy at any time, the patient is eligible to continue on Pacritinib + HMA (Part 2). Part 2 will not continue if Part 1 is stopped early. A maximum of 40 total evaluable patients (n=40) will be enrolled.

Study design: Part 1

The standard practice is to put these patients on observation, an ORR rate of about 15% is clinically relevant. The target ORR with the experimental treatment is 15%. The regimen of the Pacritinib will be considered worthy of further investigation if it elicits an increase in ORR to 15% with acceptable toxicity. A >15% therapy related non-hematological grade 3/4 toxicity rate is considered unacceptable. Thus, interim monitoring rules, assuming the prior distributions below, were constructed that meet the following two conditions,

- 1) Stop if $\text{Prob}\{p(\text{ORR}, E) < 0.15 \mid \text{data}\} > 0.975$, or
- 2) Stop if $\text{Prob}\{p(\text{TOX}, E) > 0.15 \mid \text{data}\} > 0.975$,

where $P(\text{ORR}, E)$ and $P(\text{TOX}, E)$ are the true ORR and toxicity rates for the Pacritinib, and $p(\text{ORR}, H)$ is the true ORR rate of the standard treatment. The first rule provides for stopping the study if the data suggest that it is unlikely (i.e., probability < 2.5%) that ORR rate of the Pacritinib treatment is greater than 15.0%. The second condition will stop the study early if excessive therapy-related non-hematological grade 3/4 toxicity (>15%) is highly probable (i.e., probability >97.5%) for the Pacritinib. Monitoring for toxicity and futility will not begin until 5 patients have been evaluated, and cohort size for future evaluations is 5.

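### Growth-factor use bars an HI assessment for only 2 weeks, yet HI must last 8 weeks, so improvement that was partly growth-factor supported can count towards ORR

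*Combined protocol and SAP*

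**What the plan says.** Section 5.0 (Concomitant and Excluded Therapies) states: "Erythropoietin, granulocytic or other hematopoietic colony stimulating factors for treatment of cytopenias are discouraged". They are not prohibited. If one is given, the subject "will not be eligible for a hematologic improvement (HI) response assessment within 2 weeks of administration". The same section requires all medications to be recorded.

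Table 10 in Section 10.0 sets the duration of HI: "responses must last at least 8 wk". Section 10.0 counts as response "any hematological improvement achieved any time during the duration of the therapy". Section 12.0 describes ORR as "based mainly on hematologic improvement defined by IWG-2006 criteria" and says that in Part 1 "overall response will be assessed after 1 cycle of treatment but no more than after 4 cycles of treatment; cycle length is 28 days".

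Under Section 8.0 (During Treatment), blood counts are weekly in the first course and afterwards are taken before each course. The Statistical Analysis Plan text in Section 12.0 names only drop-outs as failures and does not mention growth factors. No section requires the 8-week interval to be free of growth factor, restarts the 8 weeks after a dose, or classes an exposed patient as a non-responder.

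**The concern.** The bar is tied to the date of an assessment, while the response is defined over an interval four times as long. A patient can pass the bar at the assessment and still have received growth factor during much of the 8 weeks that the response is said to have lasted. These agents would be given for the cytopenias from which HI is measured.

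Use is foreseeable. Section 2.1 describes usual care in this population as supportive, including growth factors, and no exclusion criterion in Section 3.0 names them. There is no control arm to absorb the effect. If such responses are counted, ORR is inflated and the Part 1 futility rule has less chance of stopping an inactive regimen.

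**Working it through.** **Inputs.** Bar of 2 weeks (Section 5.0); HI duration of 8 weeks (Table 10); 28-day cycles with scheduled counts before each course after cycle 1 (Sections 4.0 and 8.0); maximum n=40, target ORR 15%, prior Beta(0.3, 1.7), futility cut-off 0.975, looks every 5 patients from n=5 (Section 12.0, Part 1).

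**1. Share of the HI interval that can be exposed.**
- Bar applied to the confirming assessment only: 8 − 2 = 6 weeks, and 6/8 = 75%.
- Bar applied to every scheduled pre-cycle count: take counts at weeks 0, 4 and 8. Growth factor may be given in the first 4 − 2 = 2 weeks of each 4-week gap and every count still clears the bar. That is 2 × 2 = 4 weeks, and 4/8 = 50%.
- Whole interval required to be free of growth factor: 0 of 8 weeks. The protocol does not say this.

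**2. The plan's own futility boundary.** Stop with x responses among n patients if P(p < 0.15 | Beta(0.3 + x, 1.7 + n − x)) > 0.975.

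| n | x = 0 | x = 1 | x = 2 | Stop at |
|---|---|---|---|---|
| 10 | 0.9732 | 0.7435 | 0.4099 | never |
| 15 | 0.9902 | 0.8765 | 0.6342 | 0 |
| 25 | 0.9985 | 0.9727 | 0.8826 | 0 |
| 30 | 0.9994 | 0.9873 | 0.9370 | 0-1 |
| 35 | 0.9998 | 0.9942 | 0.9670 | 0-1 |

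This reproduces Table 12.

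**3. Effect of a single counted response.** 1/40 = 2.5 points. Two such responses would move an observed 4/40 (10%) to 6/40 (15%), the target. At the 15-, 20- and 25-patient looks, one counted response passes the boundary of 0. If it is still the only response at n=30, the trial stops there.

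**4. Illustration under assumed rates.** An exact binomial recursion over looks at 5, 10, ..., 35 gives a futility-stop probability of 63.3% at a true ORR of 5% and 27.7% at 10%. The documents give no usage rates. Assume that a share u = 10-30% of non-responders receive growth factor and that h = 20-40% of those reach a countable HI. Counted ORR = p + (1 − p)·u·h.

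| True ORR | Counted ORR | Futility stop |
|---|---|---|
| 5% | 0.05 + 0.95 × 0.02 = 6.9% to 0.05 + 0.95 × 0.12 = 16.4% | 63.3% falls to between 47.2% and 8.2% |
| 10% | 0.10 + 0.90 × 0.02 = 11.8% to 0.10 + 0.90 × 0.12 = 20.8% | 27.7% falls to between 19.9% and 3.4% |

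These figures are for futility alone under the stated 5-patient looks. They do not come from Table 13, which also includes toxicity stopping and does not reproduce with looks every 5 patients. That is a separate matter and does not affect the exposure arithmetic in step 1.

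**The case against.** The best counter-argument is that HI lasting 8 weeks needs a qualifying count at onset as well as at the end. If the bar covers every such count, an onset seen on growth factor, or within 2 weeks after it, is already excluded. What remains is a response first seen without recent growth factor, then supported, then still present more than 2 weeks after the last dose. That confounds the maintenance of a response more than its onset. This is a fair reading and the protocol does not rule it out. It lowers the exposed share from 75% to about 50% but does not close the gap, because scheduled counts after cycle 1 are about 28 days apart.

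Second, exposure is not misclassification. The final count must still meet the HI criterion after the 2-week gap, so a false response on this route needs an effect that outlasts it. The documents give no duration of effect. This stands, and it limits the point to what the rule permits.

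Third, use is discouraged and medications are recorded, so exposed responders can be identified. That also stands, but the plan does not say how the analyst should treat them.

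A reader might infer that one false responder averts a futility stop. Table 12 does not support that: with no other response, the stop is delayed to the 30-patient look.

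**Conclusion.** The point holds as a gap in the definition of the primary endpoint. The rule as written lets HI count when up to 6 of its 8 weeks (bar on the confirming assessment only) or about 4 of 8 (bar on every scheduled pre-cycle count) were growth-factor supported. Each response counted in this way adds 2.5 points at n=40 and can pass the 15- to 25-patient futility looks.

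A reader might go further and infer that rises produced largely by growth factor will be credited to pacritinib, or that ORR is biased by a known amount. The documents do not support either. The 75% figure depends on one reading of Section 5.0, and neither frequency of use nor persistence of effect is given. The ranges for counted ORR and stopping probability rest wholly on the assumed u and h. The conclusion is that supported improvement can be counted, and the plan should settle this before responses are adjudicated.

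**What to change.** Keep the Section 5.0 bar for any listed growth factor, and add to Section 10.0: HI counts in the primary ORR only if no such agent was given from 2 weeks before the start of the 8-week interval to its end. After a dose, the 8-week clock restarts 2 weeks after the last administration, so a patient given a brief course can still qualify later. Report ORR without this restriction as a sensitivity analysis. The rule should not be narrowed to agents acting on the same lineage, because that would loosen the present bar, which applies after any listed agent.

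This changes only how responses are counted, not who may receive growth factors, and the medication data are already collected. The cost is that ORR may be somewhat lower and that a true responder given growth factor during the interval may be counted late. If the 8 weeks must end by week 16 (4 cycles × 4 weeks), such a patient may not be counted at all. After a dose, a full interval fits only if the last administration is by week 16 − 8 − 2 = 6. With a dose between weeks 6 and 8, no complete interval fits: one ending before the dose would have to start at or before day 0, and one starting after the washout would end after week 16. The plan should therefore also state whether the 16-week limit in Section 12.0 or the any-time wording in Section 10.0 governs HI.

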6.0 AGENT FORMULATION AND PROCUREMENT

Pacritinib study drug description and storage

Pacritinib for oral administration is supplied in capsules containing 100 mg as free base SB1518 in dark green or red cap/gray body size “zero” opaque hard gelatin capsules. The inactive ingredients are microcrystalline cellulose, magnesium stearate, and polyethylene glycol 8000.

Pacritinib capsules should not be opened or crushed. Direct contact of the powder in Pacritinib capsules with the skin or mucous membranes should be avoided. If such contact occurs, affected areas should be washed thoroughly with water.

Pacritinib capsules should be stored at controlled room temperature, excursions allowed from 15 to 30°C or 59 to 86°F. All study supplies must be kept in a restricted-access area.

Observed Risks

Based on the adverse effects observed in toxicity studies, as well as data from phase 1 and 2 clinical studies in patients with advanced MF, AML, and lymphoma, the investigator is advised to observe the following precautions:

- **Hematologic:** Reversible myelosuppression; leukopenia, neutropenia, thrombocytopenia, and anemia have been observed; these events are common in hematologic malignancies and may not be related to pacritinib administration. Thrombocytopenia, anemia, neutropenia, and leukopenia ADRs were more common in lymphoid than myeloid patients. Patients participating in clinical trials of pacritinib will be monitored frequently for myelosuppression. Provisions for interruption of treatment and dose reduction in the event of myelosuppression are outlined in clinical trial protocols.
- **Gastrointestinal:** Treatment with pacritinib is associated with dose-related diarrhea and nausea. Vomiting, abdominal pain, abdominal distension, anorexia, and constipation have also been reported to be related to pacritinib administration. Diarrhea and vomiting ADRs were more common in myeloid studies than lymphoid studies, but the reverse was true for constipation. Nausea was the same in both populations. Antiemetic and antidiarrheal medications should be prescribed prophylactically to control symptoms. Fluid and electrolytes should be replaced as needed to prevent dehydration. Pre-existing nausea, vomiting, and diarrhea should be adequately controlled before beginning therapy. Patients with significant GI symptoms despite optimal supportive care may have study drug interrupted or have the dose of study drug reduced per protocol.

- **Cardiac:** QTc prolongation has been reported in association with pacritinib therapy. A post-hoc review of the patients in the phase 1-2 Studies SB1518-2007-001 and SB1518-2008-003 identified 9 patients with at least one reported QTc exceeding 500 ms; all but one were treated at a pacritinib dose of ≥ 400 mg QD. Therapy was continued in most of these patients for extended periods of time after the observations of QTc prolongation. In addition, pre-study cardiac history was noted in 7 patients, and 8 patients were taking concomitant medications associated with QTc prolongation. Other cardiac TEAEs and ADRs were rare in all pacritinib-treated populations. Based on these observations, investigators are advised to exclude any patient with a baseline QTc > 450 ms and to perform routine ECG monitoring during treatment. For patients with identified changes in treatment-emergent ECG abnormalities or other cardiac events, study drug may be interrupted or the dose may be reduced per protocol.
- **Hepatic:** Animal studies suggest that pacritinib treatment may cause dose-related hepatotoxicity. There has been little evidence of hepatotoxicity in clinical trials to date. Significant increases in aminotransferases have been observed infrequently and have not been accompanied by concomitant increases in bilirubin. Most reported hepatic toxicities were seen in the myeloid population. No instances of hepatic dysfunction meeting Hy's Law criteria have been observed. Hepatic function (AST/SGPT, ALT/SGOT, alkaline phosphatase, and total bilirubin) will continue to be assessed at frequent intervals during treatment with pacritinib.
- **Renal:** Animal studies suggest that treatment may cause dose-related renal toxicity. To date, little impact on renal function has been observed in human clinical trials. Assessment of renal function (creatinine, BUN, sodium, potassium) will be undertaken frequently in patients participating in clinical trials of pacritinib.
- **General:** Additional adverse effects commonly reported during pacritinib administration have included infections, fatigue, asthenia, peripheral edema, pyrexia, and rash. Infectious ADRs were more common in lymphoid patients, while the other adverse effects were more common in myeloid patients. Bleeding and bruising complications have been reported, most of which were low grade and generally more common in the myeloid population than in the lymphoid population. Patients participating in clinical trials of pacritinib will be monitored closely for these adverse effects.

No reproductive or developmental toxicity studies have been performed; therefore, the effects of pacritinib on female and male fertility are unknown. If fertile, both males and females must agree to use effective birth control. Women of childbearing potential must use highly effective methods of birth control for the duration of study treatment and for 12 months after last dose of study drug. The contraceptive methods considered highly effective are intrauterine devices and hormonal contraceptives (contraceptive pills, implants, transdermal patches, hormonal vaginal devices, or injections with prolonged release).

No drug-drug interaction studies have been conducted with pacritinib. In vitro studies indicate that pacritinib has no significant potential to inhibit or induce CYP450 isozymes and has no significant involvement with p-glycoprotein mediated transport. Pacritinib is believed to be metabolized by CYP3A4. Therefore, caution is advised when considering the coadministration of potent inhibitors of CYP3A4 in conjunction with pacritinib. Specific exclusions are outlined in the protocols for human clinical trials of pacritinib.

Gastrointestinal Toxicity Management

Treatment with pacritinib is associated with dose-related diarrhea and nausea. Vomiting, abdominal pain, abdominal distension, anorexia, and constipation have also been reported

to be related to pacritinib administration. Diarrhea and vomiting ADRs were more common in myeloid studies than lymphoid studies, but the reverse was true for constipation. Nausea was the same in both populations. Antiemetic and antidiarrheal medications should be prescribed prophylactically to control symptoms. Fluid and electrolytes should be replaced as needed to prevent dehydration. Pre-existing nausea, vomiting, and diarrhea should be adequately controlled before beginning therapy. Patients with significant GI symptoms despite optimal supportive care may have study drug interrupted or have the dose of study drug reduced per protocol.

Study Drug Dose, Route, and Mode of Administration

Patients will be supplied with 100 mg pacritinib capsules. Two capsules should be taken twice a day at approximately the same time of day without regard of food. Dose reductions will be allowed if the Investigator determines an event is related to study treatment as per Section 5.0.

Pacritinib will be administered primarily on an outpatient basis, but may be administered as an inpatient. Vomited doses will not be made up on the same day. Unused study drug returned by the patient will be destroyed in accordance with institutional policy.

Decitabine and azacitadine may be administered by local doctor or at MD Anderson. Cycle 1 of Part 2 will be administered at MDACC. Commercial supplies of decitabine and azacitadine will be used.

Outside physician participation during treatment is acceptable. Documentation of MDACC physician communication with the outside physician will be required. Protocol required evaluations outside MDACC will be documented by telephone, fax or email. Fax and/or email will be dated and signed by the MDACC physician. Changes in HMA drug dose and/or schedule must be discussed with and approved by the MDACC PI or Investigator, or their representative prior to initiation, and will be documented in the patient record.

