3.0 PATIENT SELECTION

Inclusion criteria

1. Signed informed consent indicating that patients are aware of the investigational nature of this study, in keeping with the policies of MDACC, must be obtained prior to any study specific procedures.
2. Patients with a histologically confirmed diagnosis of MDS by World Health Organization (WHO) classification and lower-risk MDS as defined by the IPSS classification² (Low or Int-1 disease) or R-IPSS classification¹² (Very Low or Low) are eligible. Patients with MDS/MPD overlap syndromes including CMML are also eligible if they have Low or Int-1 disease per IPSS. Patients may have received MDS-directed therapy (i.e. lenalidomide), although patients with prior exposure to hypomethylating agents (e.g. 5-azacitidine or decitabine) are not eligible.
3. The interval from prior treatment to time of study drug administration is at least 1 week (except for hydroxyurea or steroid therapy) with recovery from all prior therapy-related toxicities
4. Age ≥ 18 years old.
5. Eastern Cooperative Oncology Group (ECOG) performance status of 0 to 2.
6. Adequate liver function, as evidence by serum bilirubin $\leq 2x$ the laboratory normal range (except for patients with Gilbert's Disease), or an aspartate aminotransferase (AST) or alanine aminotransferase (ALT) of $\leq 2.5x$ the upper limit of normal (ULN) or $\leq 5x$ ULN if hepatic disease involvement is present as determined by the investigator.
7. Serum creatinine (Cr) $\leq 2x$ ULN or 24-hour creatinine clearance ≥ 50 ml/min
8. Subjects of reproductive potential must agree to the use of acceptable contraceptive methods for the duration of the time on study and a further 6 months after completion of treatment. Women of childbearing potential must have a negative blood or urine pregnancy test within 72 hours of start of treatment.

Exclusion criteria

1. Subjects with any prior exposure to the hypomethylating agents (5-azacitidine or decitabine) are excluded.
2. Subjects with any prior exposure to JAK2 inhibitor therapy (i.e. ruxolitinib or prior pacritinib therapy) are excluded.

3. Any prior or coexisting medical condition that in the investigator's judgment will substantially increase the risk associated with the subject's participation in the study.
4. Psychiatric disorders or altered mental status precluding understanding of the informed consent process and/or completion of the necessary study procedures.

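### For women of childbearing potential, inclusion criterion 8 secures a shorter and looser contraception commitment (6 months) than Section 6.0 demands (12 months)

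*Combined protocol and SAP*

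**What the plan says.** Section 3.0, inclusion criterion 8, covers both sexes: "Subjects of reproductive potential must agree to the use of acceptable contraceptive methods", and the period is "for the duration of the time on study and a further 6 months after completion of treatment". The criterion does not list which methods count as acceptable.

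Section 6.0, in the text under Observed Risks, makes two statements. The first covers both sexes and gives no duration: "If fertile, both males and females must agree to use effective birth control". The second covers women only: "Women of childbearing potential must use highly effective methods of birth control", and the period runs through study treatment and then "for 12 months after last dose of study drug". Section 6.0 then names what it counts as highly effective: intrauterine devices and hormonal contraceptives.

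Neither section refers to the other on this subject, and nothing in the text available says which prevails.

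**The concern.** A woman of childbearing potential falls under both rules. Criterion 8 is the text that site staff check at eligibility, so it fixes the commitment needed for entry. That commitment ends sooner, and allows a wider or at least undefined range of methods, than Section 6.0.

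The written instruction carries much of the weight in the period in dispute:

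- Section 6.0 itself says that reproductive and developmental toxicity has not been studied and that the effect on fertility is unknown. Section 2.3 does report a fertility study in male mice, but the females in it were untreated.
- The study calendar (Table 8) schedules a pregnancy test before treatment only.
- Section 13.0 ends routine capture of serious adverse events 30 days after the last treatment. Later events are reported only if related to treatment.

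This is a patient-safety instruction that says two things. It is not a flaw in the statistical design.

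**Working it through.** The plan gives no figure to reproduce. The check sets the two rules side by side and then subtracts the durations.

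| Element | Section 3.0, criterion 8 | Section 6.0, Observed Risks |
|---|---|---|
| Who | All patients of reproductive potential | 12-month rule: women of childbearing potential only |
| Method standard | Acceptable, not defined there | Highly effective, with methods named |
| During the trial | Time on study | Study treatment |
| Afterwards | 6 months | 12 months |
| Clock starts | Completion of treatment | Last dose of study drug |
| Fertile men | 6 months, as for all | Effective birth control, no period given |

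**Gap in duration for women.** Let T be completion of treatment and D the last dose of study drug, both in months.

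- Criterion 8 ends at T + 6.
- Section 6.0 ends at D + 12.
- Gap = (D + 12) − (T + 6) = 6 − (T − D).

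If T = D, the gap is 12 − 6 = 6 months.

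**How far the starting points could move it.**

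- *Part 2.* A hypomethylating agent is given with pacritinib. If study drug means pacritinib alone, T could fall after D. Sections 4.0 and 11.0 end treatment once study drug has been stopped for more than 6 weeks. Taking that as the limit on T − D (an assumption), 6 × 7 = 42 days, and 42 / 30.4 ≈ 1.4 months. The gap is then at least about 6 − 1.4 = 4.6 months. If the hypomethylating agent counts as study drug, T = D and the gap stays at 6.
- *Time on study.* Section 4.0 adds telephone follow-up every 2 months until another cancer treatment. If time on study includes that follow-up, criterion 8 could run past T + 6. The gap would shrink, and would vanish for a woman followed to D + 12 or later. The protocol does not define the term.

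**Gap in duration for men.** Section 6.0 supplies no post-treatment period to subtract from. Criterion 8 is the only stated duration, so no conflict can be shown.

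**Direction.** A woman who uses a method on the Section 6.0 list for 12 months after the last dose also meets criterion 8, if T = D. The reverse does not hold: agreeing to criterion 8 alone does not cover the second 6 months or the stricter methods.

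**The case against.** The best defence is that Section 6.0 is programme-level background. Its precautions are introduced as advice to the investigator, and the surrounding text speaks of pacritinib trials in general. Criterion 8 would then be the trial-specific rule. This explains how the mismatch may have arisen, but it does not remove it. The contraception sentence is mandatory in wording and sits in this protocol. Unlike neighbouring items on dose changes and CYP3A4 exclusions, it does not defer to rules stated elsewhere.

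A second defence is that few patients are concerned. The trial enrols at most 40 evaluable patients, and Section 2.1 gives a median age at diagnosis of 70 years. That stands as a point about weight. The protocol gives no number of women affected, but it admits patients from age 18 and provides for pregnancy testing.

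A reader might also infer more than the documents support:

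- *That women enrolled under criterion 8 breach Section 6.0.* Criterion 8 does not tell anyone to stop at 6 months, and a woman may well follow the longer rule. What can be shown is that entry does not secure her agreement to it.
- *That patients have been told 6 months.* The consent pages are not in the material available, so their wording is unknown.
- *That the conflict in duration covers all patients.* It covers women of childbearing potential only.
- *That the gap is exactly 6 months for every such woman.* That depends on the starting points coinciding.

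**Conclusion.** The inconsistency is real and limited to women of childbearing potential. Criterion 8 secures agreement to a shorter period and a less specific method standard than Section 6.0 requires. The size is 6 months if the two starting points coincide and time on study ends with treatment. It could be somewhat less in Part 2, and less or nil if time on study takes in telephone follow-up.

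Between them the two sections also use three terms for the standard (acceptable, effective, highly effective), and only the last is defined.

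This is an inconsistency in wording with a bearing on safety. The response endpoint, the monitoring rules in Section 12.0 and the planned analyses are untouched. It should be corrected, but it does not call the design into question.

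**What to change.** Reconcile inclusion criterion 8 with the contraception text in Section 6.0 so that both state:

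- one post-treatment duration for women of childbearing potential;
- one starting point, saying for Part 2 whether it is the last dose of pacritinib, of the hypomethylating agent, or of whichever ends later;
- one method standard, with the qualifying methods listed once and cross-referenced.

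Section 6.0 should also say whether a post-treatment period applies to fertile men, so that it can be read together with criterion 8. The consent form should be checked against the reconciled text. Which duration and methods to adopt is a clinical decision for the sponsor and is not judged here.

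The cost is a wording amendment through the approval route in the Protocol Administration section. Sample size, visits and analysis do not change.
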